# 9.7.1.2.2. Compliance to patient screening and laboratory monitoring prior to and during tofacitinib treatmentIT

The screening and monitoring variables listed in Table 3 will be described and tabulated.

### 9.7.1.2.2.1. Compliance to recommendations for limitations of use

### 9.7.1.2.2.1.1. Patients with VTE risk factors

The proportion of patients with one or more risk factors for VTE, identified prior to tofacitinib initiation, will be described and tabulated overall and by individual VTE risk factor (e.g., prior VTE, recent MI). Proportions will be stratified by "RA or PsA" and "UC."

The total number of VTE risk factors identified prior to tofacitinib initiation will also be described continuously and stratified by "RA or PsA" and "UC."

The proportion of patients diagnosed with UC, one or more VTE risk factors identified prior to tofacitinib initiation, and no use of an alternative therapy (i.e., biologic) prior to tofacitinib

<sup>oo The study outcomes that contain an ADD component will *not* be assessed in Hungary or the Netherlands. The Hungarian administrative claims database is unable to estimate ADD, either directly or by proxy, due to how tofacitinib is captured in the database. In the high-budget impact medication dataset of the PHARMO Database Network (Netherlands), neither ADD nor the number of pills per prescription is captured.

<sup>pp In GKV claims, outpatient diagnoses are reported quarterly.

<sup>qq Hungary will not have a VTE Reporting Period 1. Hungary will also not have a VTE Reporting Period 2 for PsA and UC.

<sup>IT This outcome (and all sub-outcomes) will not be assessed in Sweden because the Swedish national health registers do not capture the laboratory tests of interest. In GKV claims, it may not be possible to differentiate an ALC laboratory test from an ANC laboratory test, or an ALT laboratory test from an AST laboratory test. In the PHARMO Database Network, TB screening and viral hepatitis B and C testing are not captured.

initiation whose ADD in Week 16 through Week 23, Week 24 through Week 31, Week 32 through Week 39, and Week 40 through Week 47 was >10 mg will be described and tabulated.

The proportion of patients who discontinue tofacitinib after developing one or more VTE risk factors while taking tofacitinib will be described and tabulated overall and by individual VTE risk factor (e.g., VTE, MI). Proportions will be stratified by "RA or PsA" and "UC."

The proportion of patients who continue tofacitinib after developing one or more VTE risk factors while taking tofacitinib will be described and tabulated overall and by individual VTE risk factor (e.g., VTE, MI). Proportions will be stratified by "RA or PsA" and "UC."

#### 9.7.1.2.2.1.2. Patients aged 65 years and older

The proportion of patients initiating tofacitinib aged 65 years and older at the index date without prior alternative therapy (defined as  $\geq 1$  biologic in the 12 months prior to index date), will be described and tabulated. Proportions will be presented overall and stratified by approved indication.

The proportion of patients aged 65 years, receiving tofacitinib, who have 0 prescription dispensings of tofacitinib from the time they turn 65.5 years old through the end of the follow-up period, will be described and tabulated. Proportions will be presented overall and stratified by approved indication.

The proportion of patients aged 65 years, receiving tofacitinib, who have  $\geq 1$  prescription dispensing of tofacitinib from the time they turn 65.5 years old through the end of the follow-up period and no history of alternative treatments *prior to* that tofacitinib prescription dispensing, will be described and tabulated. Proportions will be presented overall and stratified by approved indication.

The proportion of patients aged 65 years, receiving tofacitinib, who have  $\geq 1$  prescription dispensing of tofacitinib from the time they turn 65.5 years old through the end of the follow-up period and a history of alternative treatments *prior to* that tofacitinib prescription dispensing, will be described and tabulated. Proportions will be presented overall and stratified by approved indication.

### 9.7.1.2.2.1.3. Patients with CV risk factors

The proportion of patients with one or more CV risk factors, identified prior to tofacitinib initiation, will be described and tabulated overall and for each individual CV risk factor (i.e., elderly, current or past smokerx, history of diabetes, history of hypertension, history of hyperlipidaemia, history of coronary artery disease, history of chronic kidney disease, history of stable angina pectoris). Proportions will be stratified by approved indication and sex.

The proportion of patients with one or more CV risk factors, identified prior to tofacitinib initiation and no prior use of an alternative therapy (i.e., biologic), will be described and tabulated overall and for each individual CV risk factor (i.e., elderly, current or past smokerx,**Error! Bookmark not defined.** history of diabetes, history of hypertension, history

of hyperlipidaemia, history of coronary artery disease, history of chronic kidney disease, history of stable angina pectoris). Proportions will be stratified by approved indication and sex.

The proportion of patients who discontinue tofacitinib after developing one or more CV risk factors while taking tofacitinib, will be described and tabulated overall and for each individual CV risk factor (i.e., elderly, current smokerx, diabetes, hypertension, hyperlipidaemia, coronary artery disease, chronic kidney disease, stable angina pectoris). Proportions will be stratified by "RA or PsA" and "UC" and sex.

The proportion of patients who continue tofacitinib after developing one or more CV risk factors while taking tofacitinib, will be described and tabulated overall and for each individual CV risk factor (i.e., elderly, current smokerx, diabetes, hypertension, hyperlipidaemia, coronary artery disease, chronic kidney disease, stable angina pectoris). Proportions will be stratified by "RA or PsA" and "UC" and sex.

### 9.7.1.2.2.1.4. Patients with malignancy risk factors

The proportion of patients with one or more malignancy risk factors, identified prior to tofacitinib initiation, will be described and tabulated overall and for each individual malignancy risk factor (i.e., elderly, history of malignancy, current or past smokerx). Proportions will be stratified by approved indication.

The proportion of patients with one or more malignancy risk factors, identified prior to tofacitinib initiation and no prior use of an alternative therapy (i.e., biologic), will be described and tabulated overall and for individual malignancy risk factor (i.e., elderly, history of malignancy, current or past smokerx). Proportions will be stratified by approved indication.

The proportion of patients who discontinue tofacitinib after developing one or more malignancy risk factors while taking tofacitinib will be described and tabulated overall and by individual malignancy risk factor (i.e., elderly, history of malignancy, current smokerx). Proportions will be stratified by "RA or PsA" and "UC."

The proportion of patients who continue tofacitinib after developing one or more malignancy risk factors while taking tofacitinib will be described and tabulated overall and by individual malignancy risk factor (i.e., elderly, history of malignancy, current smokerx). Proportions will be stratified by "RA or PsA" and "UC."

### 9.7.1.2.2.1.5. Potential contraindicated use of tofacitinib

The proportion of patients treated with tofacitinib with potential contraindicated use will be described and tabulated overall and reported by type of contraindicated use (e.g., patients with severe hepatic impairment, pregnant patients, etc.). Note that patients may be captured in more than one type of contraindicated use category.

#### 9.7.1.2.2.1.6. Use with concomitant medications not compatible with tofacitinib

The proportion of tofacitinib patients with concomitant use of medications not compatible with tofacitinib will be reported overall and by patients with and without  $\geq 2$  tofacitinib prescription dispensings.ss Additionally, the number of overlapping days' supply of the biologic or selected potent immunosuppressant with the tofacitinib prescription dispensing will be described continuously and categorically (e.g., 1-7 days, 8-14 days, 15-21 days, 22-30 days,  $\geq 31$  days; final cut-offs to be determined after examining the distribution of the data).

9.7.1.3. Secondary Objectives 1 and 2: Describe prescribing patterns; and Describe changes in tofacitinib prescribing patterns (utilisation) following the updated recommendations and limitations for use implemented after the 2019 Article 20 referral and the 2021 signal evaluation procedurett,uu,vv,ww

#### 9.7.1.3.1. Use in patients with VTE risk factors

The proportion of patients with one or more risk factors for VTE, identified prior to tofacitinib initiation, will be described and tabulated overall and for each individual VTE risk factor (e.g., prior VTE, recent MI) for VTE Reporting Period 1, VTE Reporting Period 2, and VTE Reporting Period 3.vv Proportions will be stratified by "RA or PsA" and "UC."

The total number of VTE risk factors identified prior to tofacitinib initiation will also be described continuously for VTE Reporting Period 1, VTE Reporting Period 2, and VTE Reporting Period 3vv and stratified by "RA or PsA" and "UC."

The proportion of patients diagnosed with UC, one or more VTE risk factors identified prior to tofacitinib initiation, and no use of an alternative therapy (i.e., biologic) prior to tofacitinib initiation whose ADD in Week 16 through Week 23, Week 24 through Week 31, Week 32 through Week 39, and Week 40 through Week 47 was >10 mg will be described and tabulated for VTE Reporting Period 1, VTE Reporting Period 2, and VTE Reporting Period 3.vv

The proportion of patients who discontinue tofacitinib after developing one or more VTE risk factors while taking tofacitinib will be described and tabulated overall and for each individual VTE risk factor (e.g., VTE, MI) for VTE Reporting Period 1, VTE Reporting

ss Patients with  $\geq 2$  dispensings of tofacitinib are more likely to have taken tofacitinib for the full days' supply of the prescription as opposed to patients with only 1 dispensing of tofacitinib.

<sup>tt The study outcomes that contain an ADD component will *not* be assessed in Hungary or the Netherlands. The Hungarian administrative claims database is unable to estimate ADD, either directly or by proxy, due to how tofacitinib is captured in the database. In the high-budget impact medication dataset of the PHARMO Database Network (Netherlands), neither ADD nor the number of pills per prescription is captured.

<sup>uu In GKV claims, outpatient diagnoses are reported quarterly.

<sup>vv Hungary will not have a VTE Reporting Period 1. Hungary will also not have a VTE Reporting Period 2 for PsA and UC.

<sup>ww Hungary will not have a CV and Malignancy Reporting Period 1 or a CV and Malignancy Reporting Period 2 for PsA and UC.

Period 2, and VTE Reporting Period 3.vv Proportions will be stratified by "RA or PsA" and "UC."

The proportion of patients who continue tofacitinib after developing one or more VTE risk factors while taking tofacitinib will be described and tabulated overall and for each individual VTE risk factor (e.g., VTE, MI) for VTE Reporting Period 1, VTE Reporting Period 2, and VTE Reporting Period 3.vv Proportions will be stratified by "RA or PsA" and "UC."

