# 9. RESEARCH METHODS

## 9.1. Study design

This will be a descriptive drug utilisation study using secondary data collected from databases in Sweden, Hungary, the Netherlands, and Germany. These databases will be used to identify patients who are tofacitinib users and obtain data on patient demographics, diagnoses, prescription medication dispensings, procedures, and administered screening and monitoring tests. All results will be stratified by country and approved indication (i.e., RA, PsA, and UC), unless otherwise specified. Additionally, the proportion of patients treated with tofacitinib without evidence of an approved indication will be described and tabulated, stratified by study country.

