- Compliance to patient screening and laboratory monitoring prior to and during tofacitinib treatment, as measured by:h
  - The proportion of patients with evidence of having received the following recommended screenings *prior to* initiation of tofacitinib:
    - Creatinine (serum or urine) laboratory testing;
    - TB screening;
    - Viral hepatitis B and C screening;
    - ALC laboratory testing;
    - ANC laboratory testing;
    - Haemoglobin laboratory testing; and

<sup>g Hungary will not have a VTE Reporting Period 1. Hungary will also not have a VTE Reporting Period 2 for PsA and UC.

<sup>h This outcome (and all sub-outcomes) will *not* be assessed in Sweden because the Swedish national health registers do not capture the laboratory tests of interest. In GKV claims, it may not be possible to differentiate an ALC laboratory test from an ANC laboratory test, or an ALT laboratory test from an AST laboratory test. In the PHARMO Database Network, TB screening and viral hepatitis B and C testing are not captured.

- ALT and/or AST laboratory testing (i.e., liver function testing);
- For patients with 6 and 12 months of tofacitinib therapy, the proportion of patients with evidence of having received the following recommended monitoring *after* initiation of tofacitinib in the respective periods:
  - TB screening;
  - Viral hepatitis B and C screening;
  - ALC laboratory testing;
  - ANC laboratory testing;
  - Haemoglobin laboratory testing;
  - ALT and/or AST laboratory testing; and
  - Lipid panel (i.e., total cholesterol, high-density lipoprotein [HDL], lowdensity lipoprotein [LDL], and triglycerides [TG]) laboratory testing;
- Compliance to recommendations to limitations for use, including
  - Use in patients with VTE risk factors, as measured by:e
    - The proportion of patients with evidence of  $\geq 1$  VTE risk factors *prior to* initiation of tofacitinib, reported overall and by approved indication;
    - The number of VTE risk factors identified *prior to* initiation of tofacitinib, reported overall and by approved indication;
    - The proportion of patients with UC who have: ≥1 VTE risk factor identified *prior to* tofacitinib initiation; no use of an alternative therapy (i.e., biologic) *prior to* tofacitinib initiation; and an ADD >10 mg in Weeks 16-23, Weeks 24-31, Weeks 32-39; and Weeks 40-47 of follow-up;f

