  - The proportion of patients with evidence of ≥1 malignancy risk factors *prior to* initiation of tofacitinib and no prior use of an alternative therapy (i.e., biologic), reported overall and by approved indication;
  - The proportion of patients who discontinue tofacitinib after developing ≥1 malignancy risk factor while taking tofacitinib; and
  - The proportion of patients who continue taking tofacitinib after developing ≥1 malignancy risk factor while taking tofacitinib;

- Contraindicated use, as measured by:e
  - A patient *initiating* tofacitinib therapy if they have severe hepatic impairment;i
  - A woman *initiating* tofacitinib therapy if she is pregnant;
  - A patient *initiating* tofacitinib therapy if they have or have had TB in the prior 2 months;
  - A patient initiating tofacitinib therapy if they have or have had a serious and/or opportunistic infection in the prior 2 months; and
  - A woman *receiving* tofacitinib therapy during her pregnancy;
- Use with concomitant medications not compatible with tofacitinib, as measured by:
  - The proportion of patients receiving biologics and/or potent immunosuppressants *while taking* tofacitinib; and
  - The proportion of patients receiving a live vaccination *while taking* tofacitinib;j

The secondary outcomes of interest will be:

- Tofacitinib prescribing patterns over time;e,f and
- Changes in the prescribing patterns (utilisation) of tofacitinib following the updated recommendations and limitations for use implemented after the 2019 Article 20 referral and the 2021 signal evaluation procedure, specifically:
  - Use in patients with VTE risk factors, as measured by:e,f
    - The proportion of patients with evidence of ≥1 VTE risk factors *prior to* initiation of tofacitinib, reported overall and by approved indication and stratified by VTE Reporting Periodk

<sup>i The data sources are unable to reliably ascertain severity of hepatic impairment; thus, this sub-outcome may be overestimated.

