<sup>j This sub-outcome will not be assessed in Sweden because most vaccinations are not done in specialist care and therefore are not captured in the National Patient Register (NPR), nor are vaccines prescribed and purchased by the patients in the pharmacies and therefore are not be captured in the Prescribed Drug Register (PDR). Vaccination data are also unavailable in the PHARMO Database Network. In GKV claims, it is not possible to differentiate between live and non-live vaccines.

<sup>k Hungary will not have a VTE Reporting Period 1. Hungary will also not have a VTE Reporting Period 2 for PsA and UC.

- The number of VTE risk factors identified *prior to* initiation of tofacitinib, reported overall and by approved indication and stratified by VTE Reporting Periodk
- The proportion of patients with UC who have: ≥1 VTE risk factor identified *prior* to tofacitinib initiation; no use of an alternative therapy (i.e., biologic) *prior to* tofacitinib initiation; and an ADD >10 mg in Weeks 16-23, Weeks 24-31, Weeks 32-39; and Weeks 40-47 of follow-up, stratified by VTE Reporting Periodf,k
- The proportion of patients who discontinue tofacitinib after developing ≥1 VTE risk factor while taking tofacitinib, reported overall and by approved indication and stratified by VTE Reporting Periodk
- The proportion of patients who continue taking tofacitinib after developing ≥1 VTE risk factor while taking tofacitinib, reported overall and by approved indication and stratified by VTE Reporting Periodk
- Use in the elderly (patients 65 years and older), as measured by:
  - The proportion of patients 65 years and older with no alternative treatments *prior to* initiation of tofacitinib, reported overall and by approved indication and stratified by VTE Reporting Periodk and CV and Malignancy Reporting Periodl
  - The proportion of patients aged 65 years, receiving tofacitinib, who have 0 prescription dispensings of tofacitinib from the time they turn 65.5 years old through to the end of the follow-up period, reported overall and by approved indication and stratified by VTE Reporting Periodk and CV and Malignancy Reporting Periodl

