### 9.7.1.3.3. Use in patients with CV risk factors

The proportion of patients with one or more CV risk factors, identified prior to tofacitinib initiation, will be described and tabulated overall and for each individual CV risk factor (i.e., elderly, current or past smokerx, history of diabetes, history of hypertension, history of hyperlipidaemia, history of coronary artery disease, history of chronic kidney disease, history of stable angina pectoris) for CV and Malignancy Reporting Period 1, CV and Malignancy

Reporting Period 2, and CV and Malignancy Reporting Period 3.ww Proportions will be stratified by approved indication and sex.

The proportion of patients with one or more CV risk factors, identified prior to tofacitinib initiation and no prior use of an alternative therapy (i.e., biologic), will be described and tabulated overall and for each individual CV risk factor (i.e., elderly, current or past smokerx, history of diabetes, history of hypertension, history of hyperlipidaemia, history of coronary artery disease, history of chronic kidney disease, history of stable angina pectoris) for CV and Malignancy Reporting Period 1, CV and Malignancy Reporting Period 2, and CV and Malignancy Reporting Period 3.ww Proportions will be stratified by approved indication and sex.

The proportion of patients who discontinue tofacitinib after developing one or more CV risk factors while taking tofacitinib will be described and tabulated overall and for each individual CV risk factor (i.e., elderly, current smokerx, diabetes, hypertension, hyperlipidaemia, coronary artery disease, chronic kidney disease, stable angina pectoris) for CV and Malignancy Reporting Period 1, CV and Malignancy Reporting Period 2, and CV and Malignancy Reporting Period 3.ww Proportions will be stratified by approved indication and sex.

The proportion of patients who continue tofacitinib after developing one or more CV risk factors while taking tofacitinib will be described and tabulated overall and for each individual CV risk factor (i.e., elderly, current smokerx, diabetes, hypertension, hyperlipidaemia, coronary artery disease, chronic kidney disease, stable angina pectoris) for CV and Malignancy Reporting Period 1, CV and Malignancy Reporting Period 2, and CV and Malignancy Reporting Period 3.ww Proportions will be stratified by approved indication and sex.

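### Section 9.3.1 promises the VTE outcomes separately for RA, PsA and UC, but the analysis sections pool RA with PsA, whose mix changes between reporting periods

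*Protocol*

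**What the plan says.** The general rule in Section 9.1 of the protocol is "All results will be stratified by country and approved indication (i.e., RA, PsA, and UC), unless otherwise specified". Section 9.7.1 repeats it in similar terms.

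Section 9.3.1 then gives the reporting level outcome by outcome:

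- **Primary VTE items.** The proportion with at least one risk factor and the number of risk factors are each identified before "initiation of tofacitinib, reported overall and by approved indication". The primary discontinuation and continuation items carry no such promise.
- **Secondary VTE items.** The same two items are given before "initiation of tofacitinib, reported overall and by approved indication and stratified by VTE Reporting Period". Discontinuation and continuation follow developing at least one "VTE risk factor while taking tofacitinib, reported overall and by approved indication and stratified by VTE Reporting Period".

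The analysis sections say something else. Section 9.7.1.3.1 handles all four secondary items with "Proportions will be stratified by 'RA or PsA' and 'UC", or the same two groups for the count. Section 9.7.1.2.2.1.1 does likewise for the primary items; the number of risk factors "will also be described continuously and stratified by 'RA or PsA' and 'UC".

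The neighbouring period analyses are not pooled. Age (9.7.1.3.2), CV (9.7.1.3.3: "Proportions will be stratified by approved indication and sex") and malignancy (9.7.1.3.4) all use approved indication.

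**The concern.** The protocol fixes two incompatible table layouts for the same outcomes, so this is not a detail left open for the SAP.

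The choice has consequences for the before/after comparison. Section 9.9 says that cautious use in patients with VTE risk factors cannot be assessed directly and will be approximated by the proportion of treated patients with such risk factors before and after the 2019 materials. That proportion is tabulated by VTE Reporting Period. Section 9.2.5 excludes patients whose index dispensing precedes distribution of the original materials for their indication, and PsA was approved about a year after RA. The pooled stratum is thus almost all RA early on and contains more PsA later. If the two groups differ in how often they carry a VTE risk factor, the pooled proportion shifts even when prescribing within each indication is constant. Age over 50 alone counts as a VTE risk factor in Table 3, so an age difference between the groups would be enough. No adjustment for the mix is stated.

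**Working it through.** **1. The plan's own figures.** Section 9.5: n = 0.50 × 0.50 × 1.96² / 0.10² = 96.04, rounded up to 97 and then to 100 per indication per country. This reproduces, as do the six values in Table 5. The VTE period lengths of 26, 16 and 39 months also reproduce. Precision was therefore planned for each indication separately.

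**2. When PsA can enter.** Period 1 runs from April 2017 to May 2019. Table 2 dates the original PsA materials to July 2018 (Sweden, Germany) and September 2018 (the Netherlands).

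- Sweden, Germany: July 2018 to May 2019 = 11 of 26 months.
- The Netherlands: September 2018 to May 2019 = 9 of 26 months.
- All three: every month of Periods 2 and 3.
- Hungary: no Period 1. Period 2 is RA only, and PsA reimbursement is anticipated in Q1 2023, inside Period 3, so the shift falls between Periods 2 and 3.

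**3. PsA share of the pooled stratum.** The counts come from Table 10 (Germany, 2017-2019: RA 843, PsA 169) and Table 9 (the Netherlands, through 2019: RA 180, PsA 40). Assume constant monthly accrual to December 2019, starting in May 2017 for RA (32 months, 25 of them in Period 1) and at the PsA materials date for PsA, and the same monthly rates afterwards.

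| | Germany | Netherlands |
|---|---|---|
| RA per month | 843/32 = 26.3 | 180/32 = 5.6 |
| PsA per month | 169/18 = 9.4 | 40/16 = 2.5 |
| Period 1 RA | 659 | 141 |
| Period 1 PsA | 103 | 22 |
| PsA share, Period 1 | 13.6% | 13.8% |
| PsA share, later | 26.3% | 30.8% |
| Shift | 12.7 points | 17.0 points |

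No split by indication is given for Swedish tofacitinib users, so no share is computed there.

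**4. Effect on the pooled proportion.** Apparent change = −(later PsA share − Period 1 PsA share) × (RA prevalence − PsA prevalence). The prevalences are not in the protocol, so the gap is an assumption.

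| Assumed gap, RA minus PsA | Germany | Netherlands |
|---|---|---|
| +10 points | −1.3 | −1.7 |
| +20 points | −2.5 | −3.4 |
| +30 points | −3.8 | −5.1 |
| 0 | 0 | 0 |
| −20 points | +2.5 | +3.4 |

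For example, with assumed prevalences of 85% (RA) and 65% (PsA), the pooled figure goes from 82.3% to 79.7% in Germany and from 82.2% to 78.8% in the Netherlands. With separate RA and PsA rows, this artefact is zero by construction.

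**The case against.** **The default allows exceptions.** The general rule applies unless otherwise specified, and Section 9.7 does specify. That answers the general rule but not the explicit promise made for each outcome in Section 9.3.1. Where grouping was meant as an option, 9.3.1 says so: average daily dose may be reported by approved indication or by indication group. The VTE items have no such alternative.

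**The effect is modest and the inputs are soft.** This stands. At 82%, the 95% half-width in Period 1 is 1.96 × √(0.82 × 0.18/163) = 5.9 points in the Netherlands and, with 762 patients, 2.7 points in Germany. The artefact at a 20-point gap (3.4 and 2.5) lies inside both. It is still a systematic shift that the intervals do not reflect. The table rows also exceed their totals (Germany 843 + 169 + 190 = 1202 against 1111; the Netherlands 180 + 40 + 65 = 285 against 280), so the shares are approximate.

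**The study is descriptive.** Also true. Section 9.7.1 rules out comparative statistics, and Section 9.9 calls the before/after reading limited. But the limitations do not mention a changing RA/PsA mix within the pooled stratum.

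**Wider readings that the protocol does not support.** A reader might infer that every VTE table is pooled. The table combining dose, risk factors and no prior biologic is confined to UC. A reader might also infer that 9.3.1 is contradicted by the pooled primary discontinuation and continuation items, for example in 9.7.1.2.2.1.3 ("Proportions will be stratified by 'RA or PsA' and 'UC' and sex"). It is not: 9.3.1 promises no indication split for those primary items, whether VTE, CV or malignancy, and the CV and malignancy initiation items are already by approved indication.

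**Conclusion.** The contradiction holds for four secondary VTE items (at least one risk factor, number of risk factors, discontinuation, continuation) and for the first two primary VTE items. The change in composition follows from the protocol's own dates and exclusion rule. Its size does not: 1.3 to 5.1 points rests on constant accrual, on approximate counts from Germany and the Netherlands, and on assumed prevalence gaps of 10 to 30 points.

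A reader might infer that pooling would imitate a fall in use among patients with VTE risk factors. That requires PsA patients to carry such factors less often than RA patients, and the protocol gives no prevalence by indication. If PsA prevalence were higher, the artefact would be a rise. The supported statement is that the pooled proportion can move either way without any change in prescribing. This is worth correcting before the tables are fixed, but it does not undermine the study.

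**What to change.** In Section 9.7.1.3.1, and for the first two items of Section 9.7.1.2.2.1.1, replace the two-group stratification by RA, PsA and UC, as in Section 9.3.1. Keep the combined RA and PsA row only as a supplement, and show the PsA share of that row for each reporting period.

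Optionally, use the same three strata for the primary discontinuation and continuation items in Sections 9.7.1.2.2.1.1, 9.7.1.2.2.1.3 and 9.7.1.2.2.1.4. The reason would be consistency with Sections 9.7.1.3.3 and 9.7.1.3.4 and with the general default in Sections 9.1 and 9.7.1, not a requirement of Section 9.3.1.

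The cost is wording and a few table rows. Some PsA cells will be small: about 22 Dutch PsA patients in Period 1 under the accrual assumed above, with a 95% half-width of up to 1.96 × √(0.25/22) = 21 points. Section 9.3.1 already commits to that reporting level, and the supplementary pooled row remains for readers who want a tighter interval.
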